Following completion of tPA infusion or initiation of mechanical thrombectomy (arterial puncture), whichever occurs sooner, eligible adult subjects will receive 3K3A-APC or placebo 30 to 120 minutes later given as a 15-minute infusion. Subjects will receive another 15-minute infusion of 3K3A-APC every 12 hours (+/- 1 hour) for up to 5 total infusions. Four dose levels will be considered for this study: 120, 240, 360, and 540 µg/kg. For the purposes of this study, we assume an established background symptomatic intracerebral hemorrhage (SICH) rate of 3-6%²⁻⁷. Correspondingly, the MTD will be defined as the highest dose with a DLT rate of 10% or less. Subjects will be enrolled to 3K3A-APC dose cohorts in groups of four (three to specified treatment

dose and one to placebo). Subjects will generally be enrolled at the dose estimated from the assumed dose-response model and prior data to be closest to the MTD. However, the initial cohort will start at the lowest dose level ($120 \mu g/kg$) and the dose level may be escalated by no more than one dose between consecutive cohorts (there are no restrictions on dose level de-escalation). Intra-subject dose modification is not permitted during the study.

Prior to starting the CRM, based on a best estimate from the literature and previous studies, the four dose levels will be assigned prior probabilities as indicated in Table 3 below.

Table 3. Assumed prior probabilities of toxicity at four dose levels considered for the study:

Dose Level	120	240	360	540
Prior Probability of Toxicity	5%	7%	9%	11%

When designing a CRM, O'Quigley, Pepe and Fisher recommend using a single-parameter doseresponse model $\psi(x_i^*, a)$, which is probability of toxicity at dose x_i^* for some unknown parameter, a, which defines the shape of the dose-toxicity function. For this study, a hyperbolic tangent doseresponse model will be used, in which

$$\psi(x_i^*,a) = \left\{\frac{\tanh(x_i^*+1)}{2}\right\}^a.$$

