After each group of subjects has been treated, and their status observed as to whether or not each had a DLT, the posterior mean of *a* will be calculated. Based upon that estimate, \hat{a} , the highest dose with estimated toxicity probability, $\psi(x_i^*, a)$ less than or equal to 10% will be allocated to the next group of subjects needing treatment assignment. If this dose is more than one level higher than the previous dose allocated to a cohort, the dose will only be increased one level. After the final group of subjects is enrolled, the final MTD will be defined as the highest dose with estimated toxicity probability less than or equal to the target toxicity level of 10%.

Hence, the design will proceed as follows:

- Enroll the first 4 subjects into cohort 1.
 - Treat one of the four subjects (chosen randomly) with placebo.
 - $_{\odot}$ Treat the other three subjects with the lowest dose: 120 µg/kg.
 - Observe the number of subjects (out of the three treated subjects) that have a DLT per study definition. Any given subject who receives only one dose of study drug and does not experience a DLT will not be included in the CRM calculation (i.e. two or more doses will need to be administered to be included).
 - Based upon the observed information from the three treated subjects, refit the assumed dose-response curve.
- Initially (through version 7.1. of the protocol), the re-estimated dose-response curve using all cohorts enrolled to date was then used to determine the highest dose level of the four under consideration that has an estimated probability of toxicity less than or equal to 10%

- The next cohort of subjects is treated at the dose level specified above unless the chosen dose level is more than one level higher than the current level. If so, treat the next cohort of subjects at the next dose level above the current level.
- Based on a DSMB recommendation, this process was changed as of version 8.0 of the protocol. The basic process proceeds as described above, but once all subjects in a given cohort (n) have been enrolled, data from all prior cohorts (cohort 1, cohort 2,, cohort n-1) are used to determine the dose level of cohort n+1.

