8.3 Sample Size and Accrual

8.3.1 Primary Outcome

In order to assess the adequacy of the sample size, we conducted a simulation study to examine the ability of the study to identify the MTD under a range of assumed scenarios. The scenarios under consideration are summarized below in Table 4. The scenarios describe the full range of possibilities:

- Scenario 1 considers the case where all doses are safe (i.e., true toxicity probability is below the target threshold for each dose.
- Scenarios 2-5 consider the case where the true target toxicity level of 10% occurs at each successive dose level under consideration.
- Scenario 6 considers the case where no dose level is safe (i.e., true toxicity probably is above the target threshold for all doses.

Scenario	Description		Dose	Level		
		120	240	360	540	
1	MTD = Dose 4	0.05	0.05	0.05	0.05	
2	MTD = Dose 4	0.05	0.05	0.07	0.10	
3	MTD = Dose 3	0.05	0.07	0.10	0.15	
4	MTD = Dose 2	0.05	0.10	0.15	0.20	
5	MTD = Dose 1	0.10	0.15	0.20	0.25	
6	No MTD	0.15	0.20	0.25	0.30	

Table 4. Assumed True Toxicity Probabilities for Simulation Scenarios

The results of the simulation study are summarized in table 5, and contrasted to the results from a pure 3+3 design (which was proposed in the original version of the protocol). Below, we provide a short summary of the findings from the simulation study:

- In scenario 1, both CRM approaches and the 3+3 method select the highest dose with high probability.
- In scenarios 2-5, both CRM approaches generally do a better job at selecting the "correct" dose as the MTD. The 3+3 method does slightly better at selecting the highest dose when

it is the MTD (scenario 2). However, this comes at a cost of "overshooting" the MTD when the true MTD occurs at a lower dose – as high as 88% under scenario 5.

 In scenario 6, the CRM approaches correctly conclude that no dose satisfies the criteria of MTD over half of the time, whereas the 3+3 has a small probability of declaring no MTD and seems to select any of the four doses in a near uniform manner.

	D	0		sults of Simu				%True	
Scenario	Dose	9	6 Recommen	aea	# Su	# Subjects Allocated			
	Level						Toxicity		
		0014	0014	0.0	0.0014	0014	0.0	CRM	
		CRM		3+3	CRM		3+3		
1	None	0%	1%	1%					
	120	2%	2%	2%	8.1	11.5	3.5	5%	
	240	3%	4%	2%	5.3	8.9	3.4	5%	
	360	4%	5%	3%	5.4	8.0	3.6	5%	
	540	91%	88%	91%	42.2	32.6	45.2	5%	
2	None	1%	1%	1%					
	120	4%	4%	2%	9.3	12.4	3.4	5%	
	240	9%	9%	2%	8.3	10.8	3.4	5%	
	360	19%	19%	10%	10.4	11.4	4.4	7%	

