After each evaluable subject in a cohort is adjudicated by the SRC as having or not having a DLT, the CRM will be updated by an unblinded study statistician and independently verified by a second unblinded study statistician. Specifically, the posterior mean of a will be re-estimated using the prior probabilities from Table 1 and all evaluable data for each cohort of subjects. Subsequently, the posterior probabilities of observing a DLT at each 3K3A-APC dose, $(x_{120}, x_{240}, x_{360}, x_{540})$, can be calculated by solving the above equation for:

$$\psi(x_i^*, \hat{a}), i = 120, 240, 360, 540.$$

Based upon that estimate, the largest dose with estimated toxicity probability, $\psi(x_i^*, \hat{a})$, less than or equal to 10% will be allocated to the next cohort of randomized participants. If this dose is more than one level higher than the previous dose allocated, the dose will only be increased one level. Dose de-escalation is not subject to any restrictions. There are 22 cohorts of four subjects each planned, but fewer may be enrolled should the study meet any of the stopping criteria.

In summary, the CRM model will proceed as follows:

- Enroll the first 4 subjects into cohort 1.
 - Treat one of the four subjects (chosen randomly) with placebo.
 - Treat the other three subjects with the lowest dose: 120 µg/kg.
 - Observe the number of subjects (out of the three treated subjects) that have a DLT per the study DLT definition.
 - Determine the number of evaluable subjects in the cohort. Any given subject who receives only one dose of study drug and does not experience a DLT will not be considered “evaluable”, and will not be included in the CRM calculation (i.e., for subjects with no DLT observed, two or more doses will need to be administered to be included).
 - Based upon the observed information from the evaluable subjects in the cohort, refit the assumed dose-response curve.
- Initially (through version 7.1 of the protocol), the re-estimated dose-response curve using all cohorts enrolled to date was then used to determine the highest dose level of the four under consideration that has an estimated probability of toxicity less than or equal to 10%.
 - The next cohort of subjects is treated at the dose level specified above – unless the chosen dose level is more than one level higher than the current level. If so, treat the next cohort of subjects at the next dose level above the current level.

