- Based on a DSMB recommendation, this process was changed as of version 8.0 of the protocol. The basic process proceeds as described above, but once all subjects in a given cohort (n) have been enrolled, data from all prior cohorts (cohort 1, cohort 2, ..., cohort $n-1$) are used to determine the dose level of cohort $n+1$.
 - If enrollment is rapid such that both cohort ($n-1$) and cohort (n) are filled and awaiting DLT review, new subjects enrolled will be randomized to placebo until cohort ($n-1$) has been reviewed. (For example, if both cohort 13 and 14 are filled and awaiting review, subjects will be randomized to placebo until cohort 13 is closed and the model is rerun to determine the dose for cohort 15).
- Repeat the process.

At the conclusion of the study, the MTD will be selected using the rules specified above for the implementation of the CRM model. Specifically, the model will be run a final time using all observed data and the MTD will be defined as the highest dose with an estimated DLT rate of 10% or less based on that final model. The study will stop once the first of the following criteria have been met:

- The maximum number of cohorts (22) has been observed.

- If at any time after half of the cohorts (11) have been observed, two consecutive iterations suggest a 15% or higher toxicity rate at the lowest dose (stop for safety).
- If the study proceeds straight to the highest dose, and then observes 9 successive cohorts at the highest dose with no observed toxicity (stop and declare the highest dose the MTD).
 - Through simulation, it was determined that it would extremely unlikely to observe no DLTs after 9 successive cohorts if the true toxicity rate were 10%. Thus, after 9 cohorts we would have sufficiently determined that all doses under consideration are safe and early stopping would be justified.

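### Table 5's CRM results do not describe the written 10%-or-less dose rule; they fit a closest-to-10% choice with 'None' counting safety stops alone

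*SAP*

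**What the plan says.** SAP 7 assigns the next cohort the largest dose whose estimated toxicity probability is "less than or equal to 10% will be allocated to the next cohort of randomized participants". At the end, "the MTD will be defined as the highest dose with an estimated DLT rate of 10% or less based on that final model". Protocol 8.1.1 agrees: "the final MTD will be defined as the highest dose with estimated toxicity probability less than or equal to the target toxicity level". Escalation is capped: "If this dose is more than one level higher than the previous dose allocated, the dose will only be increased one level". After 11 cohorts, two consecutive estimates of 15% or more at 120 µg/kg stop the trial for safety.

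Protocol 8.1.1 and the Synopsis also carry a different description: "Subjects will generally be enrolled at the dose estimated from the assumed dose-response model and prior data to be closest to the MTD".

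On the prior for the model parameter, SAP 7 says only that its posterior mean "will be re-estimated using the prior probabilities from Table 1 and all evaluable data for each cohort of subjects". No prior density appears in either document.

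Table 5 gives the simulated performance of the CRM and of its lagged version (in use since protocol 8.0). On Scenario 6, Protocol 8.3.1 reads the 'None' row as follows: "the CRM approaches correctly conclude that no dose satisfies the criteria of MTD over half of the time". Both documents then argue from Table 5 that the sample size balances correct selection against undershooting and overshooting.

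**The concern.** A table of operating characteristics should come from the rule that will be run. Two features suggest this one does not.

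- A 10%-or-less cutoff and a closest-to-10% choice are different rules, and the protocol contains wording for both.
- Under SAP 7, a trial that finishes with 120 µg/kg estimated above 10% has no MTD, whether or not the 15% stop was met. Table 5's 'None' percentages look too low for that definition.

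If Table 5 describes another rule, readers are given the wrong chance of finding the MTD, of choosing too high a dose, and of concluding that no dose is acceptable. The sample-size argument would then rest on a design that is not the one written.

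**Working it through.** **Inputs.** Prior toxicity probabilities p = 5, 7, 9, 11% (SAP Table 1); one-parameter power model with the posterior mean plugged in, ψ_i = p_i^â (SAP 7); three treated subjects per cohort, at most 22 cohorts, one-level escalation cap, 15% double stop after cohort 11, early stop after 9 clean cohorts at 540 (SAP 7); true rates from Table 4. Assumed: Exp(1) prior for a, and 120 µg/kg given when no dose qualifies. With 20,000 trials per scenario the Monte Carlo standard error is at most √(0.5 × 0.5 / 20,000) = 0.35 points.

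**Where the two rules part.** Under the written rule dose i qualifies when p_i^â ≤ 0.10, that is, â ≥ ln 0.10 / ln p_i:

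- 120: 2.303/2.996 = 0.769
- 240: 2.303/2.659 = 0.866
- 360: 2.303/2.408 = 0.956
- 540: 2.303/2.207 = 1.043

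Under closest-to-10% the choice moves up a level where the two neighbouring estimates sum to 0.20: â = 0.818, 0.911 and 1.000 for 240, 360 and 540. The last is exact, since 0.09 + 0.11 = 0.20. Closest-to-10% therefore selects each higher dose sooner.

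The 15% stop needs â ≤ ln 0.15 / ln 0.05 = 1.897/2.996 = 0.633. A trial ending with â between 0.633 and 0.769 has an estimate between 10% and 15% at 120. The written rule calls that no MTD; counting stops alone calls it MTD = 120.

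**Reproducing Table 5.** With closest-to-10% for assignment and declaration, and 'None' = 15% stops only:

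- Unlagged: recommendations within 0.5, 0.9, 0.6, 1.1, 0.4 and 0.6 points (Scenarios 1–6); allocations within 0.8 subject.
- Lagged, cap counted from the last reviewed cohort: recommendations within 0.5, 1.4, 0.3, 1.2, 0.7 and 0.9 points; allocations within 1.6, 1.2, 0.2, 0.2, 0.2 and 0.1 subjects.
- Lagged, cap counted from the previous cohort (8,000 trials): recommendations within 2.2 points, but allocations off by up to 6.1 subjects (38.7 against 32.6 at 540, Scenario 1).

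**Written rule.** Ranges cover unlagged, lagged, and lagged with the cap from the last reviewed cohort.

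| Scenario | Result | Table 5 | Written rule |
|---|---|---|---|
| 1 | 540 (correct) | 88–91% | 82–85% |
| 2 | 540 (correct) | 67–68% | 58–59% |
| 3 | 360 (correct) | 31–32% | 26% |
| 4 | 240 (correct) | 42% | 36–38% |
| 5 | 120 (correct) | 54% | 30–31% |
| 6 | None (correct) | 61% | about 89% |
| 5 | None | 20–21% | 53–54% |
| 3 | above MTD | 32–33% | 25–27% |
| 4 | above MTD | 30–31% | 22% |
| 5 | above MTD | 26% | about 16% |

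The largest gap from Table 5 in each scenario is 5.9, 9.6, 7.3, 6.8, 32.3 and 27.5 points unlagged, and 4.7, 8.6, 8.4, 6.9, 33.9 and 27.7 lagged.

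**Does another prior rescue it?** Under the written rule, 19 priors were tried (gamma with mean 1, shape 0.5–30; log-normal SD 0.1–1.34; 2,000–3,000 trials per scenario). The best (log-normal SD 0.22) still misses some scenario by 13.6 points. A log-normal SD of 0.2 does give about 20% and 61–63% 'None' in Scenarios 5 and 6, but 540 in Scenario 2 then falls to 51–53%. A uniform(0,3) prior, tried separately, gives 61% for 540 in Scenario 2, the highest seen, and 48% 'None' in Scenario 5.

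**Missing fallback.** With Exp(1), at least one interim run has no dose at or below 10% in 30–32% of Scenario 1 trials and 88–90% of Scenario 5 trials. SAP 7 does not say what is assigned then, though the 15% stop and the closest-to-MTD wording point to 120.

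**The case against.** **Much of the Scenario 5 gap is scoring.** With the written dose rule but 'None' limited to safety stops, 120 is selected in about 62–65% of Scenario 5 trials, above Table 5's 54%. Scenario 5 is also a boundary case, because the true rate at 120 is exactly 10%. This is right about the size of that one cell. It does not rescue the table: SAP 7 and the table's own commentary both define 'None' as no dose meeting the criterion. Stop-only scoring also leaves cells up to about 14 points off, for example 120 in Scenario 4 at about 40% against 27%, and 540 in Scenario 2 at about 57% against 68%.

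**The closest-to-10% explanation is not proven.** The simulation code is not given. The fit needs a fairly wide prior: a log-normal SD of 0.5 misses by 10.9 points and a gamma of shape 5 by 10.6. An 11%-or-less cutoff with stop-only 'None' comes within 4.1 points. So the mechanism remains an inference; the mismatch with the written rule does not depend on it.

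**The cap wording is ambiguous.** The procedural bullets speak of the current level, which under a lag could mean the last reviewed cohort. That stands: it is a point to clarify, not a contradiction.

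**The consequences are limited.** The written rule is the safer one, the computed MTD is unchanged, and no document says that the DSMB relied on these percentages. All true, but both documents use the table to defend the sample size.

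**Conclusion.** The concern holds. Table 5 does not give the operating characteristics of the rule in SAP 7 and Protocol 8.1.1. Under the written rule correct selection is lower by about 4–24 points in Scenarios 1–5. It is higher by about 28 points in Scenario 6, and selection above the MTD is less frequent. Outside the Scenario 5 boundary case the losses in correct selection are at most about 10 points.

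The individual figures rest on the Exp(1) prior and on giving 120 µg/kg when no dose qualifies. The mismatch itself persisted under every prior tried. Confidence is medium, because the prior and code are not available and the lagged simulation is not fully recovered under the cap as written. This should be fixed, but it does not threaten the MTD calculation.

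**What to change.** 1. Confirm which rule the dose-selection program described in SAP 7 applies. If it is not 10% or less, the program and the text must be reconciled first.
2. Re-run and restate Table 5, lagged and unlagged, in Protocol 8.3.1 and SAP 9.1 under the written assignment and declaration rule. State the prior for a, and define 'None' as safety stops plus trials ending with 120 µg/kg estimated above 10%. Revise the sample-size commentary to match.
3. Add to SAP 7 and Protocol 8.1.1: *If no dose has an estimate of 10% or less and the safety stop is not met, the next cohort receives 120 µg/kg. If the final estimate at 120 µg/kg exceeds 10%, no dose met the MTD criterion.* Bring the closest-to-MTD sentence into line.
4. State whether the one-level cap in the lagged design counts from the previous cohort allocated or the last reviewed cohort, and simulate that version.

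The cost is one simulation rerun and a few sentences, plus less favourable published figures in Scenarios 1–5. The rule for computing the final MTD does not change.

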8. PRE-SPECIFIED ANALYSES OF SECONDARY OUTCOMES

8.1 Analysis of PK Parameters

An enzyme capture immunoassay method has been developed and validated by Charles River Laboratories (Reno, Nevada) for determination of 3K3A-APC activity in plasma. Brief details are included below. Tables, listings, and graphs of pharmacokinetic data will be produced by the study pharmacokineticist ([name]). These results will not be included in the FSR produced by the NeuroNEXT DCC, but will be submitted in a separate report.

PK parameters following administration of 3K3A-APC will be determined using concentration data obtained via enzyme-immunocapture assay of 3K3A-APC amidolytic activity in plasma. Based upon analysis of PK data from the Phase I study, a one-compartment IV infusion model will be used and will be parameterized in terms of the primary parameters clearance (CL) and volume of distribution (V). Secondary parameters will include C_{max} , AUC_{0-inf} , and $t_{1/2}$ and will be calculated from the primary parameters. The actual times of the beginning and end of all 5 infusions and each blood sampling time relative to the start of the first dose will be used in the modeling.

Compartmental modeling will be done using Phoenix WinNonlin Version 6.2 or higher. All analysis data and final parameter estimates for both analyses will be in SAS datasets. SAS version 9.3 or higher will be used for

data management, and to produce individual subject listing and descriptive statistics for plasma concentrations and pharmacokinetic parameters and individual subject concentration vs. time graphs. In-text graphs will be produced using SigmaPlot Version 12.5 or higher.

Observed and model-predicted plasma concentrations will be plotted on linear and semi-logarithmic axes by subject. Descriptive statistics of plasma PK parameters will be provided for each dose cohort. PK parameters will be compared among doses using descriptive statistics and graphical displays.

The analysis for the PK population will be conducted according to actual dose received. The status of the subjects will be given in a summary table by treatment group:

- Number of subjects screened
- Number of subject randomized
- Number of subjects treated
- Number of subjects who completed the study
- Number of subjects who received planned number of doses
- Number of subjects in the PK population

For pharmacokinetic data, any concentrations that are “below lower limit of quantification (BLLQ)” will be considered 0 for the purposes of analyses.

Descriptive statistics will be reported for plasma concentrations, separately for each cohort and time point. Summary tables of pharmacokinetic tables will also be produced per treatment group for each cohort. The tables will display sample size, arithmetic mean, SD, and CV%, geometric mean and CV%, and minimum, median, and maximum. The analysis will also produce graphs showing mean +/- standard error plasma 3K3A-APC concentrations versus nominal time, per regimen and treatment group (linear and semi-logarithmic). Individual subject graphs of observed- and model-predicted plasma concentrations will also be prepared. The relationship between the change from baseline in aPTT and the concurrently measured 3K3A-APC plasma concentration 1 hour after the end of infusion will also be assessed.

Finally, a listing of individual blood sampling concentration data (PK) will be generated along with a listing of antibody development results.

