Increases in the coagulation parameters, aPTT and to a much lesser extent, PT, were observed following administration of 3K3A-APC; however, the magnitudes of the changes were not considered clinically significant. Elevations above the normal range for aPTT and PT were seen in 30% and 6% of 3K3A-APC-treated subjects (doses ranging $180 - 720 \mu g/kg$ only), respectively, and in 21% and 0% of placebo subjects, respectively. The highest aPTT level observed in a single subject was 1.51 times ULN (60.4 sec) at 1 hour following infusion #4 of 360 $\mu g/kg$. The highest observed PT in a single subject was 1.02 times ULN (16.1 sec) at 1 hour following infusion #2 of 540 $\mu g/kg$. The majority of elevated values returned to within normal limits by 2 hours following each dose. No clinical signs of bleeding or bruising were observed in the study subjects despite the mild prolongations in coagulation parameters.

Repeated evaluation of blood chemistry, hematology and coagulation yielded no AEs related to placebo or active treatment. Vital signs other than blood pressure (heart rate, body temperature and respiratory rate) also did not yield any abnormalities in both treatment groups. There were no clinically significant ECG or QTc changes noted in 3K3A-APC-treated subjects.

No subject tested positive for anti-3K3A-APC antibody formation following administration of 3K3A-APC.

Dose-related systemic exposure to 3K3A-APC (measured by a validated enzyme-immunocapture assay of 3K3A-APC amidolytic activity in plasma) was observed at dose levels of $30 \ \mu g/kg$ and greater. No evidence of accumulation of 3K3A-APC was observed in the multiple-dose cohorts.

Based on compartmental modeling, mean C_{max} ranged from 249 to 5,715 ng/mL (30 and 720 µg/kg, respectively); mean values for CL (11,693 to 18,701 mL/h) and V (4,873 to 6,971 mL) were independent of dose as was the $t_{\frac{1}{2}}$ with a mean of approximately 0.25 h (range 13 to 18 min).

In summary, 540 µg/kg was tolerated in single- and multiple-dosing. The most common effects of 3K3A-APC observed in the single clinical study conducted were mild dose-related reversible increases in coagulation parameters (aPTT and PT) and mild and moderate dose-related, transient adverse events of headache, hypertension, nausea and vomiting.

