3. SECONDARY ENDPOINTS

3.1 Pharmacokinetic (PK) Properties

One secondary objective of this study is to investigate the PK properties of 3K3A-APC following tPA administration in stroke subjects. PK blood samples will be collected from approximately 40 subjects at a subset of study sites to ensure adequate sampling across all dose levels. Samples should be collected following one of the doses of 3K3A-APC at the following time points: end of infusion and 20, 40, 60, and 80 minutes after the end of infusion (5 total samples per subject). The investigator can decide which dose (dose 2-5) will be used for PK collection. Collection of samples outside of the requested nominal time will not be a protocol deviation, but it is essential that the actual time of collection be captured for analysis. Samples collected for PK will only be used for PK-related analysis and method development.

PK parameters following administration of 3K3A-APC in the study will be determined using concentration data obtained via the enzyme-immunocapture assay of 3K3A-APC amidolytic activity in plasma. PK parameters will be determined by fitting a compartmental model to each subject's data. Individual subject observed and model-predicted plasma concentration over time by treatment group will be plotted on linear and semi-logarithmic axes. Descriptive statistics of PK parameters will be provided for each dose level. Additionally, the pharmacokinetic-pharmacodynamic relationship between the change from baseline in aPTT and the concurrently measured 3K3A-APC plasma concentration will be evaluated 1 hour after the end of infusion.

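### SAP 8.1 sets concentrations below the quantification limit to 0 with no rule for geometric means, semi-log plots or the 1-hour aPTT relationship, so any post-dose value below the limit distorts or breaks them

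*SAP*

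**What the plan says.** SAP section 8.1 gives one rule for concentrations under the assay's lower limit of quantification: they "will be considered 0 for the purposes of analyses". It names no exception by time point, scale or type of analysis.

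The same section then requires:

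- Concentration summaries: "Descriptive statistics will be reported for plasma concentrations, separately for each cohort and time point".
- Tables containing "arithmetic mean, SD, and CV%, geometric mean and CV%, and minimum, median, and maximum". This follows a sentence on pharmacokinetic summary tables, so it may refer to the parameter tables, the concentration tables or both.
- Graphs of mean ± standard error concentration on linear and semi-log axes.
- Individual graphs: "Observed and model-predicted plasma concentrations will be plotted on linear and semi-logarithmic axes by subject".
- An assessment of change in aPTT against the concentration measured 1 hour after the infusion ends (also in SAP section 3.1).

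Under SAP section 3.1 and protocol section 6.4.7.1, the five samples are taken at the end of infusion and 20, 40, 60 and 80 minutes later, in about 40 subjects across all dose levels. There is no pre-dose PK sample. Neither document states the LLOQ or gives a separate rule for log-scale summaries or plots.

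**The concern.** Zero is a natural entry for a pre-dose or placebo sample, but this schedule has no pre-dose samples. In treated subjects the rule can act only while the drug is washing out, where the true value lies somewhere between zero and the LLOQ. Zero is then the lowest value possible, and it is the one value that a logarithm cannot take.

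The drug is cleared quickly: protocol section 2.5 reports a half-life "with a mean of approximately 0.25 h (range 13 to 18 min". The last two samples come several half-lives after the end of infusion, so values under the limit are plausible there. If they occur, part of the descriptive output for a secondary objective cannot be produced as written. Someone would then have to choose a workaround after seeing the data. The 60-minute sample also feeds the aPTT relationship, and aPTT at 1 hour is one of the dose-limiting toxicity criteria, so that summary carries some safety interest.

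**Working it through.** **Inputs (protocol section 2.5, Phase 1).** Mean Cmax 249 ng/mL at 30 µg/kg and 5,715 ng/mL at 720 µg/kg; mean CL 11,693 to 18,701 mL/h; mean V 4,873 to 6,971 mL; half-life about 0.25 h, range 13 to 18 min. Doses: 120, 240, 360 and 540 µg/kg.

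**1. Reproduce the stated half-life.** Half-life = ln 2 × V / CL.

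- Midpoints: 0.693 × 5,922 / 15,197 = 0.270 h = 16.2 min.
- Low ends paired: 0.693 × 4,873 / 11,693 = 17.3 min.
- High ends paired: 0.693 × 6,971 / 18,701 = 15.5 min.

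These agree with the stated value.

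**2. Share of the end-of-infusion level remaining, 2^(−t / half-life), for half-lives of 13 to 18 min.**

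- 60 min: 4.1% to 9.9%.
- 80 min: 1.4% to 4.6%.

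**3. Expected late concentrations.** Cmax per unit dose is 249/30 = 8.30 and 5,715/720 = 7.94 ng/mL per µg/kg, so roughly dose-proportional. At 120 µg/kg, Cmax is 953 to 996 ng/mL.

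- 80 min, 120 µg/kg: 953 × 0.014 ≈ 13 to 996 × 0.046 ≈ 46 ng/mL.
- 80 min, other doses: 27 to 92 (240), 40 to 137 (360) and 60 to 206 (540) ng/mL.
- 60 min: 39 to 99 ng/mL at 120 µg/kg, rising to 175 to 445 at 540.

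**4. Share of samples below the limit.** The LLOQ is not in the documents, so it is varied. Further assumptions: 30% between-subject CV on Cmax, and half-life uniform on 13 to 18 min.

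| Assumed LLOQ (ng/mL) | 80 min: 120 | 240 | 360 | 540 µg/kg | 60 min: 120 | 240 µg/kg |
|---|---|---|---|---|---|---|
| 5 | 0% | 0% | 0% | 0% | 0% | 0% |
| 10 | 1.5% | 0% | 0% | 0% | 0% | 0% |
| 20 | 29% | 1.5% | 0.1% | 0% | 0.1% | 0% |
| 50 | 93% | 46% | 17% | 3% | 27% | 0.7% |
| 100 | about 100% | 93% | 69% | 37% | 87% | 27% |

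**5. Chance that a cell contains at least one zero.** With ten treated subjects per dose (40/4, an even spread assumed), the chance is 1 − (1 − p)^10. At 80 min and 120 µg/kg this is 14% for an LLOQ of 10 (p = 0.015) and 97% for an LLOQ of 20 (p = 0.288). If a cohort means a CRM cohort, a cell holds at most three treated subjects and the chance per cell is lower.

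**6. What a zero does to each statistic.**

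- Geometric mean: 0 by the n-th root; not calculable through logs, because log 0 does not exist. The geometric CV is undefined.
- Individual semi-log plot: the point cannot be placed.
- Arithmetic mean: lowered by less than p × LLOQ. For an LLOQ of 20 at 80 min and 120 µg/kg that is under 0.288 × 20 = 5.8 ng/mL, against about 24 ng/mL expected with a 15-min half-life.
- Mean ± SE on a log axis: usually still drawable. With values 0, 0 and 20, mean and SE are both 6.7, so the lower bar reaches zero and cannot be drawn. The mean itself is lost only if all values are zero.
- Fitted parameters: CL, V, Cmax, AUC and half-life stay positive, so their geometric means are defined. With zeros kept in the fit, simulated median half-life lay between about 6% below and 2% above the true value.

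**The case against.** The strongest reply is that the problem is conditional and may never arise. With an LLOQ of 5 ng/mL no dose is affected, and with 10 ng/mL only 1.5% of the 80-minute samples at 120 µg/kg are. Phase 1 also makes a high limit unlikely. It described exposure from 30 µg/kg upward, with a half-life that did not depend on dose. From 249 ng/mL, a limit of 100 would be crossed after log2(2.49) = 1.32 half-lives, or 17 to 24 minutes, which leaves little curve to fit. This is inference, but it is sound, and the bottom row of the table should carry little weight. It does not exclude limits near 20.

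Second, the sentence listing the geometric mean may concern only parameter tables, where nothing fails. That reading is open. The semi-log plots of individual data and the 1-hour aPTT relationship are affected on either reading.

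Third, PK is descriptive here, is reported outside the final study report and has no decision rule. Medians, minima and individual listings would let a reader see the zeros. This stands, and it keeps the point minor.

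A reader might also infer that the late-time statistics are bound to be undefined, that the semi-log mean graphs cannot be drawn, or that the PK parameters are compromised. The documents support none of these. Without the LLOQ, no late sample is shown to fall below it; the mean graphs fail only in extreme cells; and the fitted parameters change little.

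**Conclusion.** The concern holds in conditional form. The blanket zero rule does not fit the log-scale output that the same section may require for concentrations and does require for plots, and no fallback is given. Wherever a treated subject's sample falls below the limit, the affected summaries are zero, not calculable or pulled downward. The cells most at risk are 80 minutes and, to a lesser extent, 60 minutes at the lower doses. At 80 minutes and 120 µg/kg the share affected runs from about 0% to 93% for assumed limits of 5 to 50 ng/mL.

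These shares rest on dose-proportional Cmax, the assumed 30% CV and uniform half-life, and healthy-volunteer kinetics carrying over to stroke patients. If 13 to 18 minutes describes dose-group means, individual half-lives vary more widely than assumed here. The consequence is confined to secondary descriptive PK reporting; dose selection by the CRM does not use it. It is a minor point, worth settling before the data are seen.

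**What to change.** Replace the single rule in SAP section 8.1, for post-dose samples in treated subjects, with the following:

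- State the LLOQ, and report the number of values below it for each dose and time point.
- For concentration tables, show the geometric mean and CV% as not calculable when more than half the values are below the limit; otherwise use a pre-stated substitution such as LLOQ/2.
- Omit these points from semi-log plots and say so in a footnote.
- Treat them as missing or censored in the compartmental fit, and state how they are handled in the 1-hour aPTT relationship.
- Keep zero for placebo samples only.
- Say whether the geometric mean is meant for concentrations, parameters or both.

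The cost is a few lines of SAP text and a small programming change. No data collection changes. LLOQ/2 is itself a convention, which is why the count below the limit should appear beside every summary that uses it.
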